The preponderance of data supporting this approach is from the melanoma field. In particular, a number of groups have shown that MAPK inhibition leads to increased melanoma antigen expression, decreased immunosuppressive cytokines, and increased trafficking of CD8+ T-lymphocytes. Additionally, it appears that BRAF inhibitors with or without MEK inhibitors are capable of triggering this phenomenon, though these findings dissipate in the setting of acquired, BRAF-inhibitor resistance. It has been well described that a common tissue and tumor response to lymphocytic infiltration is the upregulation of PDL1 that then inhibit these invading T-cells through interaction with their PD1 receptor. In melanoma, the BRAF-inhibitor associated infiltration is associated with increased tumor/stromal PDL1 expression. Dual inhibition of BRAF and PD1 has been shown to be associated with more profound and durable responses in animal models of melanoma.

We propose to test the hypothesis that induction molecularly targeted therapy triggers a favorable tumor microenvironment to augment the effects of maintenance PD1 targeting with pembrolizumab in two cohorts: BRAF mutant and BRAF-wild-type melanoma. This proposal represents a unique opportunity to test the effectiveness of combined immune and molecularly targeted therapy in two distinct subsets based on preclinical and clinical data. The successful completion of this study will:

1. Determine the immunologic effects of oncogene targeted therapy on tumor microenvironment
2. Prove the concept that abbreviated molecularly targeted therapy will augment the effectiveness of pembrolizumab maintenance therapy

Study Objectives:

Primary Objective:

Document the rate of clinical benefit (SD/PR/CR per RECIST) of abbreviated

CONFIDENTIAL

This document is confidential. Do not disclose or use except as authorized.

molecularly targeted therapy in combination with pembrolizumab in patients with unresectable and/or metastatic melanoma. A subject will have achieved clinical benefit if there is evidence of CR, PR, or SD at the time of the 24-week scan and the subject has not resumed targeted therapy.

Secondary Objectives:

1. To describe progression free survival (PFS) and 1 year overall survival (OS) of abbreviated molecularly targeted therapy in combination with pembrolizumab in patients with metastatic melanoma.
2. To define the effects of targeted and the combination of immune and molecularly targeted therapy on tumor microenvironment

[figure not shown]
Study Design:

A Simon 2-stage design will be implemented for each disease cohort. Patients will be treated with two-week lead-in of molecularly targeted therapy (MTT), followed by two 3 week cycles of combined targeted therapy (MTT) and pembrolizumab (at dose of 200 mg IV every three weeks), followed by maintenance single-agent pembrolizumab in all patients with RECIST defined stable disease (SD), partial response (PR), and complete response (CR). MTT *only will be resumed* if patients develop symptomatic or radiographic evidence of progression. If patients do not develop evidence of progressive disease (PD), then they will continue maintenance single-agent pembrolizumab for up to two years. In each cohort, patients will be accrued to first stage of the Simon design. If a prespecified number of patients maintain SD/PR/CR off MTT but on pembrolizumab at the 24-week time point, then the second stage of the two-stage design will be opened. (Please see details in statistical section) Biopsies will be performed on all patients enrolled to the first stage of the Simon two-stage for each cohort. These will be obtained at baseline and after the two-week lead-in. A third biopsy obtained after the completion of induction therapy will be obtained if feasible. An optional biopsy at time of disease progression will also be performed.

CONFIDENTIAL

This document is confidential. Do not disclose or use except as authorized.

SCHEMA

WT = wild-type; MT = mutant

Key Eligibility:

- Participants must have histologically confirmed metastatic or unresectable melanoma.
- Participants must have BRAFV600-mutation status known.
- Participants must have measurable disease.
- Age greater than or equal to 18 years.
- Participants must have disease amenable to and be willing to undergo serial core or excisional biopsies of a tumor lesion(s).
- ECOG performance status ≤ 1 (see Appendix A).
- Participants must have normal organ and marrow function as defined below:
- Participants not previously treated with BRAF inhibitors (vemurafenib, dabrafenib, encorafenib), MEK inhibitors (selumetinib, trametinib, binimetinib, cobimetinib), and/or anti-PD1/PDL1 monoclonal antibodies for metastatic or unresectable disease. Any other prior therapy *will be* allowed (including ipilimumab, adjuvant anti-PD1 therapy, high-dose IL-2).
- Has a diagnosis of immunodeficiency or is receiving systemic steroid therapy or any other form of immunosuppressive therapy within 7 days prior to the first dose of trial treatment.

CONFIDENTIAL

This document is confidential. Do not disclose or use except as authorized.

- Participants with symptomatic brain metastases will be excluded from this clinical trial. Subjects with asymptomatic, stable brain metastases and/or who have been previously treated for these conditions that are asymptomatic in the absence of corticosteroid therapy are allowed to enroll. Brain metastasis must be stable with verification by imaging (brain MRI completed at screening demonstrating no current evidence of progressive brain metastases).
- No symptomatic or untreated leptomeningeal disease.

Number of Patients & Centers

Total number of patients: 50

Sample Size Justification:

This trial will provide preliminary estimates of toxicity and efficacy and will be based on parallel Simon two-stage designs according to disease cohort. The rate of clinical benefit (CBR), defined as the rate of patients who have CR/PR/SD at week 24 while remaining off targeted therapy after induction, will be the primary efficacy endpoint. For each disease cohort, the Simon two-stage design is based on a type-I error rate of 0.1, at least 85% power, and a total sample size of 25 subjects. A complete safety assessment is planned to coincide with the review of clinical benefit at the end of the first stage.

For both cohorts, the null hypothesis of a true CBR of 0.50 will be tested against a one-sided alternative CBR of 0.75. The benchmark CBR rate of 0.50 is based on the results of the Keynote 001 trial in patients with refractory or first-line malignant melanoma treated with pembrolizumab (Robert, ASCO 2016) that reported a CBR of 0.51 regardless of BRAF mutation status. A short course of MAPK-targeted therapy in addition to pembrolizumab would be considered worthy of further investigation if there is evidence of an improvement in CBR to 0.75. Fourteen (14) subjects that are evaluable for the primary endpoint (defined as receiving at least 1 dose of dabrafenib/trametinib/pembrolizumab combination therapy prior to treatment discontinuation for any reason.) will be enrolled in the first stage, and if 8 or fewer subjects with clinical benefit are observed, then enrollment will stop. If there are 9 or more subjects with clinical benefit, then an additional 11 subjects will be enrolled, for a total of 25. The null hypothesis will be rejected if a total of 16 or more subjects with clinical benefit are observed in 25 subjects. This design yields power of 86% (target type II error of 0.15) when the CBR rate is 0.75. If the null hypothesis is true, the probability is 0.79 that enrollment to a cohort will stop at the end of the first stage. This high probability of stopping under the null was chosen to require strong evidence of benefit before opening the second stage.

Clinical benefit rates will be presented with 90% confidence intervals based on the method of Atkinson and Brown, which allows for the two-stage design.

All reported adverse events will be summarized as part of the early safety review at the

CONFIDENTIAL

This document is confidential. Do not disclose or use except as authorized.

end of the first stage. With 14-15 subjects per disease cohort, there is high probability of observing at least one event if a toxicity has an incidence of at least 10%. If the true incidence of an unexpected or severe toxicity is 10% or greater, the probability is at least 0.75 that one or more subjects will experience the toxicity during the early safety monitoring period.

The distribution of secondary endpoints of PFS and OS will be based on the method of Kaplan-Meier. ORR within each disease cohort will be estimated by the number of subjects with a best response of CR or PR (per RECIST) and presented with exact 90% confidence intervals. For sample sizes of 25 per disease cohort, the confidence intervals will be no wider than 0.35.

Correlative studies will be based on tumor biopsies and will assess changes in biomarkers due to OTT. PD-L1 expression will be classified as positive or negative according to IHC. Pre- versus post-OTT PD-L1 expression will be compared using McNemar's test. Changes in T cell subtypes and in co-stimulatory molecules will be summarized using descriptive methods

CONFIDENTIAL

This document is confidential. Do not disclose or use except as authorized.

TABLE OF CONTENTS

SCHEMA	5
1. OBJECTIVES.....	10
1.1 Study Design.....	10
1.2 Primary Objectives.....	10
1.3 Secondary Objectives.....	10
2. BACKGROUND.....	10
2.1 Study Disease(s).....	10
2.2 IND Agents.....	12
2.3 Rationale.....	33
2.4 Correlative Studies Background.....	34
3. PARTICIPANT SELECTION.....	36
3.1 Inclusion Criteria.....	36
3.2 Exclusion Criteria.....	38
- Note: Subjects with \leq Grade 2 thyroiditis and/or hypophysitis are an exception to this criterion and may qualify for the study.....	39
3.3 Inclusion of Women and Minorities.....	41
4. REGISTRATION PROCEDURES.....	41
4.1 General Guidelines for DF/HCC Institutions.....	41
4.2 Registration Process for DF/HCC Institutions.....	42
5. TREATMENT PLAN.....	42
5.1 Treatment Regimen.....	42
5.2 Pre-Treatment Criteria.....	43
5.3 Agent Administration.....	44
5.4 General Concomitant Medication and Supportive Care Guidelines.....	45
5.5 Criteria for Taking a Participant off Protocol Therapy.....	51
5.6 Duration of Follow Up.....	53
5.7 Criteria for Taking a Participant Off Study.....	54
5.8 Contraception.....	54
6. DOSING DELAYS/DOSE MODIFICATION criteria.....	56
6.1 Pembrolizumab Dose Modifications.....	56
6.2 Dabrafenib + Trametinib Dose Modifications.....	58
7. ADVERSE EVENTS: LIST AND REPORTING REQUIREMENTS.....	74
7.1 Expedited Adverse Event Reporting to the Overall PI and Merck.....	74
7.2 Expedited Reporting to the Food and Drug Administration (FDA).....	75
7.3 Expedited Reporting to Hospital Risk Management.....	75
7.4 Routine Adverse Event Reporting.....	76

CONFIDENTIAL

This document is confidential. Do not disclose or use except as authorized.

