Pembrolizumab is a potent and highly selective humanized monoclonal antibody (mAb) of the IgG4/kappa isotype designed to directly block the interaction between PD-1 and its ligands, PD-L1 and PD-L2. KeytrudaTM (pembrolizumab) has recently been approved in the United States for the treatment of patients with unresectable or metastatic melanoma and disease progression following ipilimumab and, if BRAF V600 mutation positive, a BRAF inhibitor.

CONFIDENTIAL

This document is confidential. Do not disclose or use except as authorized.

2.2.1.2 Summary of nonclinical and clinical studies.

A phase 1/2, multipart study is being conducted to evaluate the combination of the approved doses of pembrolizumab and dabrafenib and trametinib for *BRAF*V600E/K-mutant advanced melanoma. Results presented at the American Society of Clinical Oncology (ASCO) Annual Meeting June 3-7, 2016 on the nonrandomized phase 1, dose-finding part of KEYNOTE-022 showed Median days on therapy: 115 (range, 4-524). DLTs were reported in 3 out of 14 DLT-evaluable patients. Overall, 4 (26.7%) patients discontinued because of treatment-related AEs; there were no treatment-related deaths. Potentially immune-mediated AEs were reported in 6 (40.0%) patients, and included 2 cases of hyperthyroidism (1 grade 1, 1 grade 2), 2 cases of hypothyroidism (grade 1), 2 cases of uveitis (1 grade 1, 1 grade 2), and 1 case each of autoimmune hepatitis (grade 3), severe skin reactions (grade 3), and pneumonitis (grade 2). Based on observed DLTs and the AE profile, no additional dose levels were opened; pembrolizumab 2 mg/kg Q3W + dabrafenib 150 mg BID + trametinib 2 mg QD was the MTD.

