This trial has two planned cohorts, BRAFV600 mutant (cohort 1) and BRAF-wild-type melanoma (cohort 2). Treatment commences with 2 weeks of MTT (dabrafenib plus trametinib in cohort 1, trametinib in cohort 2), then two 3 weeks cycles of concomitant MTT and pembrolizumab, followed by single-agent pembrolizumab thereafter. Serial biopsies will be performed prior to MTT, and (if feasible) following the 2-week lead-in of MTT, and (if feasible) following six weeks of combination immune therapy and MTT. An optional biopsy at time of disease progression will also be performed. This trial represents a unique opportunity to not only test the effectiveness of combined immune and MTT, but also to determine which patients are most likely to benefit from this approach and, more importantly, to begin to understand why patients do or do not benefit. This valuable information that may lead to the next wave of combinatorial therapy in melanoma that involves MTT, anti-PD1 therapy, and other agents that target critical mediators of adaptive or innate resistance to combined MTT and pembrolizumab. Due to a recent shortage of research grade dabrafenib and trametinib, we plan to use commercially availability dabrafenib and trametinib. Since we cannot guarantee supply of "off-label" trametinib for cohort 2, we will open cohort 1 initially and consider

CONFIDENTIAL

This document is confidential. Do not disclose or use except as authorized.

opening cohort 2 in mid-2017, after more data is available for MEK inhibitors in patients with BRAF wild-type melanoma.

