13.4 Analysis of Secondary Endpoints

PFS and OS: The distributions of secondary endpoints of PFS and OS will be based on the method of Kaplan-Meier. Medians of the distributions of PFS and OS will be estimated and presented with 90% confidence intervals based on log(-log(endpoint)) methodology. One-year estimates of OS will also be presented using the same methods.

Early Safety Review: An early, comprehensive safety review will occur at the end of the first stage of the Simon two-stage design and will take place when one cohort has reached the end of its respective first stage according to the Simon design. Since we do not anticipate that adverse events will differ according to BRAF mutation status, all available safety data will be combined from the two cohorts, resulting in an early safety review for up to 28 patients. All reported AEs will be summarized.

For a sample of 28 patients, there is high probability of observing at least one event if a toxicity has an incidence of at least 5%. If the true incidence of an unexpected or severe

toxicity is 5% or greater, the probability is at least 0.75 that one or more patients out of 28 will experience the toxicity during the early safety monitoring period. If the true incidence of unexpected or severe toxicity is 1% or less, the probability is 0.25 or less that at least one patient of 28 will experience the toxicity during the early safety monitoring period. 0 summarizes the probabilities of observing at least one patient with a severe or unexpected toxicity during the initial safety review for a range of true incidence rates.

Table 13.1. Operating Characteristics of Early Safety Monitoring

True Incidence of Unexpected or Severe Toxicity	Probability of Observing One or More Patients with Toxicity among First 28
1%	0.25
3%	0.57
5%	0.76
8%	0.90
9%	0.93
10%	0.95
15%	0.99

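### Section 13.4 plans one pooled early safety review where the synopsis and Section 13.1 read as one per cohort, so cohort 2 may lack a stage-1 review and Table 13.1 may overstate detection

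*Combined protocol and SAP*

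**What the plan says.** Two descriptions of the early safety review stand side by side.

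- **Synopsis (Sample Size Justification) and Section 13.1 (Design).** Both introduce the Simon design as applying to each disease cohort, and both go on to say: "A complete safety assessment is planned to coincide with the review of clinical benefit at the end of the first stage". The synopsis then gives the size of the review: "With 14-15 subjects per disease cohort, there is high probability of observing at least one event" when the incidence is 10% or more, with a stated probability of at least 0.75.
- **Section 13.4 (Early Safety Review).** There is one review, which "will take place when one cohort has reached the end of its respective first stage according to the Simon design". Its content is pooled: "all available safety data will be combined from the two cohorts, resulting in an early safety review for up to 28 patients". The reason given is "Since we do not anticipate that adverse events will differ according to BRAF mutation status". Table 13.1 then gives detection probabilities for 28 patients only.

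Section 2.3 bears on which description matters. It says "we will open cohort 1 initially and consider" opening cohort 2 in mid-2017, once more data on MEK inhibitors in BRAF wild-type disease are available. It also gives the cohorts different targeted regimens: dabrafenib plus trametinib in cohort 1, trametinib alone in cohort 2.

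**The concern.** The two descriptions lead to different conduct. Under the synopsis and Section 13.1, each cohort has a safety assessment at the end of its own first stage. Under Section 13.4, the first cohort to finish stage 1 triggers the only review named, and the other cohort contributes whatever it has by then. With a staggered opening that could be few patients or none, and cohort 2 would then move from stage 1 to stage 2 without a safety review of its own.

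Pooling does not make up for this. The premise in 13.4 concerns mutation status, but the cohorts also differ in treatment. Section 6.2.2, for example, ties pyrexia to dabrafenib, which cohort 2 does not receive. The combination safety data summarised in Section 2.2.1.2 are for the three-drug regimen. A review made up of cohort 1 patients says little directly about pembrolizumab with trametinib alone.

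The operating characteristics are also at stake. The 28 in Table 13.1 is a maximum, reached only if both cohorts have 14 patients on treatment when the review is triggered.

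**Working it through.** **Inputs.** 14 evaluable patients per cohort in stage 1 (synopsis, Section 13.1); 14-15 per cohort for the synopsis safety claim; up to 28 pooled (Section 13.4); incidences from Table 13.1; accrual of 2 patients per month for the whole study (Section 13.2).

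**Formula.** For true incidence p and n patients, P(at least one event) = 1 - (1 - p)^n.

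**Step 1: reproduce the plan's figures, then set n = 14.**

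| True incidence | Table 13.1 (n = 28) | Recomputed, n = 28 | n = 14 |
|---|---|---|---|
| 1% | 0.25 | 0.245 | 0.13 |
| 3% | 0.57 | 0.574 | 0.35 |
| 5% | 0.76 | 0.762 | 0.51 |
| 8% | 0.90 | 0.903 | 0.69 |
| 9% | 0.93 | 0.929 | 0.73 |
| 10% | 0.95 | 0.948 | 0.77 |
| 15% | 0.99 | 0.989 | 0.90 |

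Table 13.1 is arithmetically correct for 28 patients. With 14, the 5% entry is 1 - 0.95^14 = 0.512.

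**Step 2: check the synopsis claim.** At 10%, 1 - 0.90^14 = 0.771 and 1 - 0.90^15 = 0.794, so at least 0.75 is right for 14-15 patients. With 13 patients it is 1 - 0.90^13 = 0.746, so 14 is the minimum.

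**Step 3: vary cohort 2's contribution to a single review triggered by cohort 1.** The documents do not give this number, so the rows are assumed values across the possible range.

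| Cohort 2 patients at the review | Pooled n | Pooled, 5% incidence | Cohort 2 alone, 10% incidence |
|---|---|---|---|
| 0 | 14 | 0.51 | 0 |
| 6 | 20 | 0.64 | 0.47 |
| 14 | 28 | 0.76 | 0.77 |

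Only the last row delivers both the Table 13.1 figure and the synopsis figure.

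**Step 4: see how a zero contribution could arise.** Section 5.1 counts the 24 weeks from the first pembrolizumab dose in Week 3, and the matching scan precedes Week 27, 26 weeks after Week 1. If all accrual (2 per month) goes to cohort 1, 14 patients take 7 months, about 30 weeks, and the review falls at about 30 + 26 = 56 weeks from the first patient. At 1 per month it is about 61 + 26 = 87 weeks. If cohort 2 opens later than that, it contributes nobody.

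**The case against.** The best defence is that the per-cohort review is already in the plan. The synopsis and Section 13.1 both place the sentence after a statement about each disease cohort, and the synopsis sizes the review per cohort. Section 13.4 could be read as describing only the first, pooled look. This stands to the extent that a reader who infers that cohort 2 definitely has no review goes further than the documents allow: that follows from 13.4 alone. But 13.4 is where the trigger, the pooling and the operating characteristics are set out, and it mentions no second review.

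Other oversight exists. Section 12.2 has the data and safety monitoring committee review toxicity up to four times a year, or more often if required. Section 13.1 promises monitoring throughout, and Section 7.1 requires serious events to be reported within 24 hours. A reader might infer that the stage-1 review is the only safety checkpoint; these provisions show that it is not. However, the committee's frequency is a ceiling, and no cohort-specific look is stated.

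Cohort 2 was only to be considered. If it never opens, no cohort is missed, but the review then has 14 patients and Table 13.1 does not describe it.

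A reader might also infer that the review comes too late to matter, since the Week 27 scan is 18 weeks after Week 9, when the last stage-1 patient leaves the combination phase. The documents do not support the conclusion that it can change nothing for stage-1 patients. They may stay on pembrolizumab for up to two years and may resume targeted therapy after progression, and the review covers all reported adverse events. It also precedes stage 2 in the cohort that triggers it. Holding it when patient 14 reaches Week 9 would not alter scheduled stage-1 combination exposure either. An extra look at seven patients, or a comparison with published dose-limiting toxicity (which this protocol does not define), would be a matter of preference.

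**Conclusion.** The plan contradicts itself on whether the early safety review is held once, pooled, or once in each cohort. Followed literally, Section 13.4 can leave cohort 2 with no review at the end of its own first stage, and it can reduce the probability of seeing a 5% toxicity from the stated 0.76 to 0.51. The size of the loss depends on how many cohort 2 patients have been treated when cohort 1 triggers the review, which the documents do not fix: 0.51 is the value with none, and 0.76 needs all 14. The calculation takes 14 treated patients per cohort and independent events with a common incidence. The conclusion concerns the number and content of the reviews. It does not extend to their being tied to the 24-week readout.

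**What to change.** - In Section 13.4, state that the safety review is held at the end of stage 1 in each cohort, and align the wording with the synopsis and Section 13.1.
- At each review, show adverse events by cohort as well as pooled, because the targeted regimens differ.
- Give Table 13.1 for n = 14 beside n = 28 (for n = 14: 0.51 at 5% and 0.77 at 10%), and say that 28 is reached only when both cohorts have contributed 14 patients.

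The cost is one additional safety summary from adverse event data already being collected, plus a less favourable stated detection probability. No extra patients, visits or procedures are needed.
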